9.7.2.1 Sub-cohorts

The PHARMO Database Network consists of databases which differ in geographical catchment area. Data from GP records and inpatient dispensings are available for different sub-cohorts of the source population, which is based on the outpatient pharmacy dispensing database.

General practitioner data will be used as an additional source for identification of the indication of study drug use in the drug utilization analysis and to identify renal status in the safety analysis.

To determine the renal status of patients primary care information and hospital discharge diagnoses will be used. For the subset of patients with GP data, eGFR values (when available) allow classification of the GFR. In the total subset, ICD-9 hospital discharge diagnoses related to renal impairment will be used (Table 12):

In addition, use or non-use of medication used by patients with advanced renal disease is available. Patients will then be characterised as:

End-stage renal disease

- a code for dialysis (V45.1 or V56) given within one year before index date.

Advanced renal disease

- a diagnosis of chronic renal failure (585) given 3 years or more before index date or
- any diagnosis of renal disease (see list) before index in combination with use of phosphate binding drugs, sodium bicarbonate or erythropoietic drugs within one year before index date.
- not being categorized as end stage renal disease (see above)

Mild renal disease

- any diagnosis of renal disease (see ICD-9 list) before index
- not being categorized as end stage or advanced renal disease (see above)

No renal disease

- none of the above

Grouped by renal status, data will be analysed to determine:

- initial indication for rivaroxaban
- rivaroxaban dose received
- crude incidences (calculated as described above) of primary safety outcomes and outcomes related to effectiveness by renal function and by dose

Inpatient dispensing data will be used to follow patients from the date that rivaroxaban or standard of care is started in hospital. The occurrence of an intracranial haemorrhage, gastrointestinal bleeding or urogenital bleeding during hospitalization will be determined on the basis of discharge diagnoses and, if feasible, medical chart review.

It is likely that a potential misclassification of renal failure will be more pronounced in mild renal failure whereas severe forms of renal failure most likely will be readily identified.

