9.2 Setting

Study drug users will be selected from the outpatient pharmacy database. This database records all outpatient dispensings from primary and secondary care in a well-defined geographic area. All study drug users living in this area will be captured in the database. All patients aged 2 years and above who have been registered in the database for at least 1 year before the index date will be included. A sub-population will be defined of patients for whom GP recorded information is also available.

The enrolment period will start on December 10, 2011 (the day after rivaroxaban received first marketing authorization in the Netherlands for the ‘treatment of DVT and long-term secondary prevention of recurrent DVT and PE’). End of enrolment will be 31 December 2017 and end of follow-up will be 31 December 2018. Interim reports will be provided for data collected 2 and 4 years after the date that rivaroxaban receives reimbursement approval for DVT treatment (see [Section 6](#) for detailed milestones). The characteristics of the two study cohorts in the first year and subsequent years of the enrolment period will be compared.

The drug utilization analysis ([Section 8.1.1](#)) will be performed in the sub-population captured by both the outpatient pharmacy database and the GP database, in order to enrich the data for the assignment of indication of use.

The Adverse Outcomes analysis (Sections [8.1.2](#) and [8.2](#)) will be performed in the full rivaroxaban cohort (outpatient pharmacy database with outcomes available from Medical Register), using the dosing as a proxy for the indication when this information is not available, and in the subcohort of comparator drug users captured by both the outpatient pharmacy database and the GP database.

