673.21	Obstetrical blood-clot embolism, delivered, with or without mention of antepartum condition
673.22	Obstetrical blood-clot embolism, delivered, with mention of postpartum complication
673.23	Obstetrical blood-clot embolism, antepartum condition or complication
673.24	Obstetrical blood-clot embolism, postpartum condition or complication

ICD-9-CM, International Classification of Diseases Ninth Revision, Clinical Modification.

Table 10. ICD-9-CM codes for ischaemic stroke

ICD-9-CM code	Description
433.0	Occlusion and stenosis of basilar artery
433.1	Occlusion and stenosis of carotid artery
433.2	Occlusion and stenosis of vertebral artery
433.3	Occlusion and stenosis of precerebral arteries mult/bilat
433.8	Occlusion and stenosis of precerebral arteries, spec
433.9	Occlusion and stenosis of precerebral arteries, unspec
434.0	Cerebral thrombosis
434.1	Cerebral embolism
434.9	Occlusion of cerebral artery, unspec
435.0	Basilar artery syndrome
435.1	Vertebral artery syndrome
435.2	Subclavian steal syndrome
435.8	Transient ischemic attack, spec.
435.9	Transient ischemic attack, unspec.
436	Acute but ill-defined cerebrovascular disease

ICD-9-CM, International Classification of Diseases Ninth Revision, Clinical Modification.

Table 11. ICD-9-CM codes for myocardial infarction (MI)

ICD-9-CM code	Description
410.0	MI, acute, anterolateral
410.1	MI, acute, anterior, NOS
410.2	MI, acute, inferolateral
410.3	MI, acute, inferoposterior
410.4	MI, acute, other inferior wall, NOS
410.5	MI, acute, other lateral wall
410.6	MI, acute, true posterior
410.7	MI, acute, subendocardial
410.8	MI, acute, spec.
410.9	MI, acute, unspec.

ICD-9-CM, International Classification of Diseases Ninth Revision, Clinical Modification.

Table 12 ICD-9-CM codes related to renal impairment

ICD-9-CM code	Description
250.4	Diabetes with renal manifestations
249.4	Secondary diabetes mellitus with renal manifestations
403	Hypertensive chronic kidney disease
404	Hypertensive heart and chronic kidney disease
581	Nephrotic syndrome
583.81	Nephritis and nephropathy, NOS, in diseases classified elsewhere
585	Chronic kidney disease (no subcodes available)
586	Renal failure, unspecified
593.6	Postural proteinuria
791.0	Proteinuria
V42.0	Kidney transplant
V45.1	Renal dialysis status
V56	Encounter for dialysis and dialysis catheter care

ICD-9-CM, International Classification of Diseases Ninth Revision, Clinical Modification.

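### Section 9.7.2.1 sends chronic renal failure codes under 3 years old and dialysis codes over 1 year old to the mild renal class by default

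*Protocol*

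**What the plan says.** Section 9.7.2.1 of the Protocol sorts patients by diagnosis codes and medication.

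- End-stage: "a code for dialysis (V45.1 or V56) given within one year before index date".
- Advanced, if not end-stage, by either of two routes. Route 1 is "a diagnosis of chronic renal failure (585) given 3 years or more before index date". Route 2 is "any diagnosis of renal disease (see list) before index in combination with use of phosphate binding drugs, sodium bicarbonate or erythropoietic drugs" in the year before index (called marker drugs here).
- Mild: "any diagnosis of renal disease (see ICD-9 list) before index", subject to "not being categorized as end stage or advanced renal disease (see above".
- None: everyone else.

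The code list is Table 12 in Annex 3. It contains 585, described as "Chronic kidney disease (no subcodes available", and also proteinuria (791.0), kidney transplant (V42.0) and both dialysis codes (V45.1, V56).

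On history, section 9.2 says that patients "registered in the database for at least 1 year before the index date will be included". No look-back for diagnosis codes is stated. In the GP subset, eGFR may be used where it is available. Section 9.7.2.1 closes by expecting misclassification mainly in mild renal failure, while "severe forms of renal failure most likely will be readily identified".

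**The concern.** Mild is a residual class. It takes every listed renal code that does not meet a stricter test, whatever that code says about severity. Two kinds of patient who may have serious kidney disease can therefore land there: those with a recent chronic renal failure code, and those whose dialysis code is more than a year old.

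Patients with decreased renal function are a named population of special interest in section 8.2. Section 9.7.2.1 reports indication, rivaroxaban dose, and crude incidences of the primary safety and effectiveness outcomes by renal class. If the mild class holds a mix of proteinuria, recent chronic renal failure and past dialysis, its dose distribution and event rates cannot be read as those of mild disease. The sensitivity analyses in section 9.7.2.2 concern the start and stop of treatment and do not test the renal classes.

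**Working it through.** The plan gives no figure on this point to reproduce, so the check is a reading of the rule followed by an illustrative range.

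**Step 1: apply the rule to example patients.** Each has only the codes and drugs shown.

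| Patient | End-stage? | Route 1? | Route 2? | Class |
|---|---|---|---|---|
| 791.0 (proteinuria) only | no | no | no | mild |
| First 585 code 2 years before index, no marker drug | no | no | no | mild |
| First 585 code 4 years before index, no marker drug | no | yes | no | advanced |
| First 585 code 2 years before index, marker drug in prior year | no | no | yes | advanced |
| V45.1 coded 2 years before index, no marker drug | no | no | no | mild |
| V56 coded 6 months before index | yes | – | – | end-stage |

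Rows 1 and 2 share a class. Rows 2 and 3 differ only in the age of the code, and since 585 carries no subcodes, that age is not a measure of stage. Row 5 follows because V45.1 and V56 are on the Table 12 list. Such a patient leaves the mild class only with a marker drug in the prior year or a 585 code at least 3 years old.

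**Step 2: record length.** A patient with less than 3 years of available diagnosis records cannot meet Route 1, whatever the true date of diagnosis. The row 3 patient, observed for only 2 years, would appear as row 2.

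**Step 3: how large might this be?** The documents give neither the time since the first 585 code nor the use of marker drugs. Assume, for illustration only:

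- the earliest 585 code is spread uniformly over an available look-back of L years;
- a share d of patients whose code is under 3 years old used a marker drug in the prior year;
- patients with dialysis coded in the prior year are left out.

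Share of 585 patients labelled mild = min(1, 3/L) × (1 − d).

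| L (years) | d = 0 | d = 20% | d = 40% | d = 60% |
|---|---|---|---|---|
| 1 to 3 | 100% | 80% | 60% | 40% |
| 5 | 60% | 48% | 36% | 24% |
| 6 | 50% | 40% | 30% | 20% |
| 10 | 30% | 24% | 18% | 12% |

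For example, L = 5 and d = 20% give 3/5 × 0.8 = 0.48. The share exceeds one half only if L < 6 × (1 − d) when L is at least 3 years, or d < 50% when L is shorter.

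**The case against.** Several points on the other side are fair.

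- **There is a second route.** A reader might infer that 585 counts as advanced only after 3 years. That is not the rule: the marker-drug route has no 3-year condition, and a recent dialysis code leads to end-stage. This stands, and it limits the problem to patients who have neither.
- **Pharmacy registration is not diagnosis look-back.** The 1-year minimum concerns the outpatient pharmacy database. Outside the GP subset, 585 codes come from the national hospital register, and the documents do not say that registration limits how far back those records reach. Section 9.4 also mentions average follow-up of ten years in the network. This stands too: it is possible, but not shown, that class depends on length of registration. However, the ten-year figure is not a guaranteed look-back for this cohort, and none is stated.
- **The plan expects misclassification in mild disease.** It does, but it places the difficulty there and treats severe disease as easy to find. The rule can put severe disease into mild.
- **eGFR is already planned.** It exists only in the GP subset and only where recorded. Sections 9.2 and 9.4 run the outcomes analysis in the full rivaroxaban cohort, so rivaroxaban users without GP data rely on codes. No step reconciles the two classifications.
- **Reach is limited.** Renal class feeds descriptive tables and crude incidences and is not in the adjustment list for the rate ratios in section 9.7.2. This stands.
- **Calling every 585 advanced would be no better.** Correct. With no stage in the code, that would exchange one misclassification for another.

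**Conclusion.** The point holds for the default to mild. Followed exactly, section 9.7.2.1 labels as mild a patient whose 585 codes are all under 3 years old, with no marker drug and no dialysis code in the prior year. It does the same to a patient whose dialysis code is over 1 year old, unless a marker drug or a 585 code at least 3 years old applies. This needs no assumption. It contaminates the mild class in the dose and crude-incidence tables, and it does not fit the expectation that severe forms will be readily found. That expectation is not wholly wrong, since recent dialysis and marker-drug users are identified.

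The size is unknown. A reader might infer that most 585 patients end up in mild. The documents do not support that: the illustrative share runs from 12% (L = 10, d = 60%) to 100% (L up to 3, d = 0), and every input to it is assumed. A reader might also infer that risk in advanced disease is hidden. That is not shown either: the advanced class loses patients but keeps the long-standing and drug-treated cases, and nothing establishes that its rate is diluted.

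**What to change.** Make four changes to section 9.7.2.1:

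1. Report patients whose 585 codes are all under 3 years old, with no marker drug and no dialysis code in the prior year, as a separate class of chronic renal failure, stage unknown, instead of mild.
2. Do not let a dialysis code older than 1 year default to mild. Assign it to a higher or separate class, with a stated rule that takes account of a kidney transplant code (V42.0).
3. State one diagnosis look-back and apply it to every patient, so that class does not depend on record length. Say how far back the hospital discharge records reach.
4. Cross-tabulate the code-based classes against eGFR in the GP subset and report the agreement.

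All of this uses data the study already plans to hold. The cost is wording, changed date conditions, and one more, possibly small, class that makes the tables slightly sparser.

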- The prevention of venous thromboembolism (VTE) in adult patients undergoing elective hip or knee replacement surgery (recommended dose: 10 mg rivaroxaban od for 35 days following hip replacement surgery and 14 days following knee replacement surgery).
- Co-administered with acetylsalicylic acid (ASA) alone or with ASA plus clopidogrel or ticlopidine, for the prevention of atherothrombotic events in adult patients after an acute coronary syndrome (ACS) with elevated cardiac biomarkers (recommended dose 2.5 mg bid).

As is the case with other anticoagulants, clinical studies of rivaroxaban have identified haemorrhage as an important safety outcome ([Lassen et al. 2008](#); [Turpie et al. 2009](#)). A post-authorization safety study programme is planned for several European countries. The aim of this document is to summarize the design of a population-based study to characterise new users of rivaroxaban, assess patterns of drug utilization, including adherence to label recommendations, and to assess the risk of bleeding associated with rivaroxaban treatment in comparison with treatment with standard of care, in routine clinical practice in the Netherlands, for DVT/PE treatment, SPAF and ACS. For DVT/PE treatment and SPAF, standard of care is treatment with a vitamin K antagonist (acenocoumarol or phenprocoumon), and for the secondary prevention of ACS, standard of care is antiplatelet drug(s) such as low-dose acetylsalicylic acid, clopidogrel, dipyridamole, prasugrel, ticlopidine and ticagrelor. The standard of care treatments for ACS will require at least dual antiplatelet and be analysed as combination treatment, irrespective of the individual drug combinations used.

8 Research questions and objectives

This post-authorization study was designed to assess patient characteristics and patterns of drug utilization and to quantify outcomes related to safety and effectiveness in new users of rivaroxaban compared with new users of standard of care.

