8.2 Secondary objective(s)

- To study the occurrence of hospitalization for bleeding events not specified as primary safety outcomes (“other bleeding”) in comparison with individuals receiving current standard of care (secondary safety outcome).
- To study the occurrence of non-infective liver disease (secondary safety outcome).
- To study outcomes related to effectiveness (DVT/PE, ischaemic stroke, myocardial infarction).
- To study all-cause mortality.
- To conduct sub-group analysis of safety and effectiveness outcomes in populations of special interest:
 - patients with decreased renal function
 - elderly patients
 - patients with cardiovascular comorbidities e.g. hypertension or diabetes.

9 Research methods

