9.3 Variables

9.3.1 Patient characteristics and drug utilization

Descriptive variables of drug utilization will be presented only for the subpopulation captured by both the outpatient pharmacy database and the GP database, as only in this subpopulation sufficient information for the assignment of the indication of use is available. The following characteristics, including risk factors/potential confounders for the outcomes under study, will be presented for comparison between the two cohorts:

- age and sex distribution at index date 
- dose of index drug at index date (not available for vitamin K antagonists as dosing is determined in anticoagulation clinics) 

- dispensed amount (can be used to estimate duration of treatment) ✓
- where available based on hospital discharge diagnosis or from available GP notes, diagnosis associated with the prescribing of the index drug (where not available, dose and duration of index drug will be used as a proxy for the associated diagnosis among rivaroxaban users). Hospital discharge diagnoses and procedures will be identified within 4 weeks before until 7 days after the index date and GP diagnosed will be identified during the index month or in the month before the index date.
- proportion of patients defined as naïve, non-naïve, recent switchers and distant switchers ✓
- number of pregnant women at index date (if communicated by midwife or gynaecologist) ✓
- number of pregnancies after index date (if communicated by midwife or gynaecologist) ✓
- type of other anticoagulant use before the index date among the non-naïve group ✓
- use of specific prescribed medications both in the year before the index date and following the index date, confirming the ACS indication: antiplatelet drugs (low-dose acetylsalicylic acid, clopidogrel, dipyridamole, prasugrel, ticlopidine and ticagrelor); ✓

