9.7.2 Safety and effectiveness outcomes

The two cohorts (of first-time users of rivaroxaban and first-time users of standard of care) will be followed up from the index date until 12 months after the end of the enrolment period for potential outcomes (safety and effectiveness). For each outcome, the first hospitalization for that outcome during the follow-up period will be identified. A separate follow-up will be performed for each of the outcomes.

For all outcomes (for DVT/PE treatment, SPAF and ACS), crude incidence rates will be estimated in both cohorts, using an as-treated approach. In this, person–time will be categorized into current, recent, past and non use. Current use will refer to person–time up to 7 days after the end of supply of the index drug, recent use will refer to person–time up to 90 days after the end of current use, past use will include all person–time contribution after the end of recent use up to 1 year after the end of current use, non-use will include all remaining time person–time contribution after past-use until end of follow-up.

Age- and sex-adjusted rate ratios with 95% CIs will be estimated for each of the three adverse outcomes comparing rivaroxaban with standard of care using Poisson regression analysis. Where numbers and data permit, adjustment will be made for relevant co-medication (described in the drug utilization section), indication and previous hospitalization for bleeding.

As a general strategy, no data imputation strategies will be applied to supplement missing data. The requirement for inclusion is complete data for critical variables such as exposure to rivaroxaban or standard of care and hospitalizations for bleedings or any other outcome event; otherwise this individual is not eligible to be a member of the study population. However, missing values may occur for potential confounder or effect modifying variables. In this case, individuals with missing values will be kept in the analysis and a separate category will be created for missing values of that variable. In sub-analyses to evaluate confounding or effect modification by variables with a large proportion of missing values, the evaluation will be considered to be conducted on the subset with complete data for the variable of interest.

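### The renal subgroup objective rests on crude incidences only; no age- and sex-adjusted estimate by renal class is specified

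*Protocol*

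**What the plan says.** - **Objective.** Protocol 8.2 includes the secondary objective "To conduct sub-group analysis of safety and effectiveness outcomes in populations of special interest". The first of its three groups is "patients with decreased renal function". The overall aim, in the opening of Section 8, is "to quantify outcomes related to safety and effectiveness in new users of rivaroxaban compared with new users of standard of care".
- **Analysis by renal status.** Section 9.7.2.1 lists three outputs: the starting indication, the rivaroxaban dose, and "crude incidences (calculated as described above) of primary safety outcomes and outcomes related to effectiveness by renal function and by dose".
- **What the cross-reference means.** Section 9.7.2 states that "crude incidence rates will be estimated in both cohorts, using an as-treated approach".
- **Adjusted analysis.** The same section also plans a model for the drug comparison: "rate ratios with 95% CIs will be estimated for each of the three adverse outcomes comparing rivaroxaban with standard of care using Poisson regression analysis". These ratios are to be adjusted for age and sex. Where data allow, "adjustment will be made for relevant co-medication (described in the drug utilization section), indication and previous hospitalization for bleeding". Renal status is not on that list, and the model is not specified by renal class.
- **Data.** Section 9.4 says that age and sex are in every record. Sections 9.2 and 9.4 take the full rivaroxaban cohort but only those comparator users who also have GP data. Under 9.7.2.1, eGFR comes from the GP subset and hospital codes cover everyone.
- **Dose.** Section 9.3.1 says that dose is "not available for vitamin K antagonists as dosing is determined in anticoagulation clinics".

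**The concern.** The protocol adjusts its main comparison for age and sex as a minimum, then drops that adjustment for a named secondary objective. A higher crude bleeding rate in impaired patients may reflect their age. A difference between drugs within a renal class may reflect different age mixes in the two cohorts. The result could suggest a renal signal that is not there, or hide one that is.

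The by-dose rates have a further problem that the document itself shows. Section 7 ties dose to indication, and 9.2, 9.4 and 9.7.1 use dose as a stand-in for indication. Crude rates by dose therefore partly compare indications.

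Table 1 gives regulatory review as the reason for strengthening the renal analyses, so these results are likely to be read closely.

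**Working it through.** **1. The plan's own figure.** Section 9.5 gives 12,000 and 48,000 person-years at 5 per 1000, to exclude a ratio of 1.5 with 80% power. Alpha is not stated; I assume 5% two-sided. The rivaroxaban share is 12,000/60,000 = 0.2.

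Events = (1.96 + 0.84)² / [0.2 × 0.8 × (ln 1.5)²] = 299. Then 299/0.005 = 59,800 person-years, which matches the stated 60,000. With 300 events the power is 80.2%. The study size reproduces and is not affected by this point. It is used below only to judge precision.

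**2. Age alone, between renal classes.** The documents give no age distribution by renal class and no age rate ratio, so every input here is assumed. Let p1 be the share of older patients (say 75 or over) among the impaired, p0 the share among the unimpaired, and R the event rate ratio of older to younger. With no true renal effect:

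crude ratio = (1 − p1 + p1R) / (1 − p0 + p0R)

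| p1 vs p0 | R = 1.5 | R = 2 | R = 3 |
|---|---|---|---|
| 0.50 vs 0.40 | 1.04 | 1.07 | 1.11 |
| 0.60 vs 0.40 | 1.08 | 1.14 | 1.22 |
| 0.60 vs 0.30 | 1.13 | 1.23 | 1.38 |
| 0.75 vs 0.30 | 1.20 | 1.35 | 1.56 |
| 0.80 vs 0.30 | 1.22 | 1.38 | 1.63 |
| 0.80 vs 0.25 | 1.24 | 1.44 | 1.73 |

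Lowest: 1.25/1.20 = 1.04. Highest: 2.60/1.50 = 1.73.

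**3. Age's share when a renal effect exists.** Let c be the crude ratio from step 2. The share of the crude log ratio due to age is ln c / (ln c + ln RR), where RR is the true renal ratio. I took RR = 1.2, 1.5 and 2, the three values of R, and the mixes 0.50 vs 0.40, 0.60 vs 0.30 and 0.80 vs 0.30, which makes 27 scenarios. The share runs from 6% (RR 2, R 1.5, 0.50 vs 0.40) to 73% (RR 1.2, R 3, 0.80 vs 0.30). It exceeds half in 6 of the 27.

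**4. Age alone, between drugs within a renal class.** The formula is the same, with p1 for rivaroxaban, p0 for the comparator and a true drug ratio of 1.

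| p1 vs p0 | R = 1.5 | R = 2 | R = 3 |
|---|---|---|---|
| 0.50 vs 0.50 | 1.00 | 1.00 | 1.00 |
| 0.50 vs 0.60 | 0.96 | 0.94 | 0.91 |
| 0.50 vs 0.70 | 0.93 | 0.88 | 0.83 |
| 0.40 vs 0.70 | 0.89 | 0.82 | 0.75 |

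The direction is also assumed. If rivaroxaban users were the older group, the ratios would invert, up to 1/0.75 = 1.33.

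**5. Precision within a class.** The planned events are 12,000 × 0.005 = 60 and 48,000 × 0.005 = 240. Suppose a renal class holds a share s of person-years and has m times the planned rate. Then SE = √[1/(60sm) + 1/(240sm)] and power to exclude 1.5 = Φ(ln 1.5/SE − 1.96).

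- s = 0.05, m = 1 (3 and 12 events): power 9%; upper 95% limit 3.54 if the observed ratio is 1.
- s = 0.30, m = 2 (36 and 144 events): power 59%; upper limit 1.44.

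**The case against.** **The outputs are descriptive.** The 8.2 subgroup bullet does not state a between-drug comparison, whereas the bullet on other bleeding does. Section 9.7.2.1 lists the crude rates beside indication and dose, as a profile. This stands as a reading of the bullet, and crude rates are a legitimate output. But the overall aim is comparative, and these rates are the only outcome result specified by renal class.

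**Other text leaves room for modelling.** Section 9.7.2 mentions sub-analyses of confounding and effect modification, and 9.7.2.2 says that unexpected biases can be dealt with later. Neither names renal status or commits to a model, and confounding by age is expected. Models by subgroup are often left to an analysis plan, but here the protocol itself fixes the measure as crude.

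**An adjusted estimate would be imprecise.** This is true under the assumptions of step 5 (9% to 59% power). It argues for showing the interval, not for leaving out the adjustment.

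**Age and sex adjustment does not remove every problem.** This stands. The rivaroxaban cohort is the full pharmacy population and the comparators come from the GP subcohort, so renal class may be ascertained differently by drug. The by-dose rates would also remain confounded by indication after adjustment for age, sex and renal class.

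**The gap is wider than renal status.** This also stands: effectiveness outcomes have no adjusted ratio specified even overall.

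**Conclusion.** The point holds as a weakness in a method that the protocol states. Crude incidence is the only outcome measure specified by renal class, although the adjusted model is already planned and its two basic covariates are in every record. Under the assumed inputs, age alone moves a crude ratio between renal classes to between 1.04 and 1.73, and a crude drug ratio within a class from 1 to as low as 0.75. The upper part of the first range exceeds the ratio of 1.5 that the study is sized to exclude. The documents do not show where in these ranges the truth lies.

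A reader might infer two stronger conclusions that the documents do not support:

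- **That the renal results would mostly show age.** No figure in the protocol supports this, and age explains more than half of the crude log ratio in only 6 of 27 assumed scenarios.
- **That the two drugs cannot be compared by renal class.** The cross-reference leads to crude rates in both cohorts, so an unadjusted comparison is possible. Only for dose against vitamin K antagonists is there no counterpart, and no model would supply one.

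**What to change.** In 9.7.2.1, keep the crude rates and add the following:

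1. Age- and sex-standardised rates by renal class.
2. For the primary safety outcomes, age- and sex-adjusted rate ratios of rivaroxaban to standard of care by renal class, with 95% confidence intervals. Take them from the 9.7.2 Poisson model with a drug-by-renal-class term, where numbers permit.
3. For this comparison, one source for renal class in both cohorts: either hospital codes and medication for everyone, or eGFR within the GP subset only.
4. Rates by dose shown within indication and labelled descriptive.

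The cost is a short addition to the text and a few extra model runs. Intervals in small renal classes will be wide, and restricting to the GP subset would widen them further.
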